13. DEFINITION OF END OF TRIAL

13.1. End of Trial in All Participating Countries

End of trial in all participating countries is defined as database lock.

14. SPONSOR DISCONTINUATION CRITERIA

Premature termination of this study may occur because of a regulatory authority decision, change in opinion of the IRB/EC, or investigational product safety problems, or at the discretion of Pfizer. In addition, Pfizer retains the right to discontinue development of *C difficile* vaccine at any time.

If a study is prematurely terminated, Pfizer will promptly notify the investigator. After notification, the investigator must contact all participating subjects and the hospital pharmacy (if applicable) within 28 days. As directed by Pfizer, all study materials must be collected and all CRFs completed to the greatest extent possible.

15. PUBLICATION OF STUDY RESULTS

15.1. Communication of Results by Pfizer

Pfizer fulfills its commitment to publicly disclose clinical trial results through posting the results of studies on www.clinicaltrials.gov (ClinicalTrials.gov), the European Clinical Trials Database (EudraCT), and/or www.pfizer.com, and other public registries in accordance with applicable local laws/regulations.

In all cases, study results are reported by Pfizer in an objective, accurate, balanced, and complete manner and are reported regardless of the outcome of the study or the country in which the study was conducted.

www.clinicaltrials.gov

Pfizer posts clinical trial US Basic Results on www.clinicaltrials.gov for Pfizer-sponsored interventional studies (conducted in patients) that evaluate the safety and/or efficacy of a

Pfizer product, regardless of the geographical location in which the study is conducted. US Basic Results are submitted for posting within 1 year of the primary completion date (PCD) for studies in adult populations or within 6 months of the PCD for studies in pediatric populations.

PCD is defined as the date that the final subject was examined or received an intervention for the purposes of final collection of data for the primary outcome, whether the clinical study concluded according to the prespecified protocol or was terminated.

EudraCT

Pfizer posts European Union (EU) Basic Results on EudraCT for all Pfizer-sponsored interventional studies that are in scope of EU requirements. EU Basic Results are submitted for posting within 1 year of the PCD for studies in adult populations or within 6 months of the PCD for studies in pediatric populations.

www.pfizer.com

Pfizer posts Public Disclosure Synopses (clinical study report synopses in which any data that could be used to identify individual patients has been removed) on www.pfizer.com for Pfizer-sponsored interventional studies at the same time the US Basic Results document is posted to www.clinicaltrials.gov.

15.2. Publications by Investigators

Pfizer supports the exercise of academic freedom and has no objection to publication by the principal investigator (PI) of the results of the study based on information collected or generated by the PI, whether or not the results are favorable to the Pfizer product. However, to ensure against inadvertent disclosure of confidential information or unprotected inventions, the investigator will provide Pfizer an opportunity to review any proposed publication or other type of disclosure of the results of the study (collectively, "publication") before it is submitted or otherwise disclosed.

The investigator will provide any publication to Pfizer at least 30 days before it is submitted for publication or otherwise disclosed. If any patent action is required to protect intellectual property rights, the investigator agrees to delay the disclosure for a period not to exceed an additional 60 days.

The investigator will, on request, remove any previously undisclosed confidential information before disclosure, except for any study- or Pfizer product-related information necessary to the appropriate scientific presentation or understanding of the study results.

If the study is part of a multicenter study, the investigator agrees that the first publication is to be a joint publication covering all investigator sites, and that any subsequent publications by the PI will reference that primary publication. However, if a joint manuscript has not been submitted for publication within 12 months of completion or termination of the study at

all participating sites, the investigator is free to publish separately, subject to the other requirements of this section.

For all publications relating to the study, the institution will comply with recognized ethical standards concerning publications and authorship, including Section II - "Ethical Considerations in the Conduct and Reporting of Research" of the Uniform Requirements for Manuscripts Submitted to Biomedical Journals, <http://www.icmje.org/index.html#authorship>, established by the International Committee of Medical Journal Editors.

Publication of study results is also provided for in the CSA between Pfizer and the institution. In this section entitled Publications by Investigators, the defined terms shall have the meanings given to them in the CSA.

If there is any conflict between the CSA and any attachments to it, the terms of the CSA control. If there is any conflict between this protocol and the CSA, this protocol will control as to any issue regarding treatment of study subjects, and the CSA will control as to all other issues.

## 1. VERSION HISTORY

The statistical analysis plan (SAP) Version 1 for Study B5091008 is based on the protocol dated 08 January 2018. The first SAP amendment (Version 2) is based on protocol amendment 1 dated 08 November 2018. This SAP amendment (Version 3) is updated to align with some changes to the analysis as mentioned in Table 1.

**Table 1. Summary of Major Changes in SAP Amendments**

SAP Version	Change	Rationale
1	Not Applicable	Not Applicable
2	[REDACTED]	[REDACTED]
3	Minor updates in Sections 3.4.3, 3.5.1, 3.5.3.1, 4.2, 4.3, 6.1.3, and 6.4.	
CCI
 
 
• Adverse events (AEs) will be summarized from day of first dose rather than from signing of the informed consent document (ICD).
 
• Analysis of AEs during the 30 minutes immediately after dosing was deleted because time-of-collection data are not available.
 
• Clarification was added to the duration calculations for reactogenicity events, based on FDA comments for the study data standardization plan.
 
• Immunogenicity analysis using the modified intent-to-treat (mITT) population will be limited based on the relative size of the mITT population.
 
• Clarifications on the populations for analysis of reactogenicity and AEs were added.
 

## 2. INTRODUCTION

This SAP provides the detailed methodology for summary and statistical analyses of the data collected in Study B5091008. This document may modify the plans outlined in the protocol; however, any major modifications of the primary endpoint definition or its analysis will also be reflected in a protocol amendment. Any major deviations from the methods specified in this document and the protocol will be discussed in the clinical study report.

### 2.1. Study Objectives

#### Primary Immunogenicity Objective:

- To demonstrate that the immune responses induced by 3 lots of *Clostridium difficile* vaccine are equivalent, as measured by *C. difficile* toxin A- and toxin B-specific neutralizing antibody levels 1 month after the third vaccination when administered in a 3-dose regimen to healthy adults 65 to 85 years of age.

## **Primary Safety Objective:**

- To evaluate the safety of *C. difficile* vaccine when administered in a 3-dose regimen to healthy adults 65 to 85 years of age, as measured by the number and percentage of subjects reporting local reactions and systemic events, adverse events (AEs), and serious adverse events (SAEs).

CCI

## **2.2. Study Design**

### **2.2.1. Description**

This is a Phase 3, placebo-controlled, randomized, observer-blinded study to evaluate the lot consistency, safety, tolerability, and immunogenicity of an aluminum hydroxide (AlOH)-containing *C. difficile* vaccine (200 µg total toxoid) administered as a 3-dose regimen at Months 0, 1, and 6 in healthy adults 65 to 85 years of age.

Approximately 1316 healthy adults, 65 to 85 years of age, will be randomized into 1 of 4 groups in a 1:1:1:1 ratio (Lot 1: Lot 2: Lot 3: placebo). Subjects withdrawn from the study after randomization will not be replaced, regardless of the reason for withdrawal.

### **2.2.2. Number of Subjects**

In order to meet the immunogenicity primary objective, the study sample size estimate is based upon the evaluation of lot-to-lot consistency on the toxin A- and toxin B-specific neutralizing antibody in terms of geometric mean concentrations (GMCs) 1 month after the third vaccination (Month 7). A 2-fold equivalence margin is used for the study. Assuming the inherent difference for toxin A- and toxin B-specific neutralizing antibody responses is no more than 0.2 (in logarithmic scale) between any 2 lots and the common standard deviations for toxin A- and toxin B-specific neutralizing antibodies are 0.899 and 1.485 (natural log value), respectively (based on the standard deviations for toxin A and toxin B at Month 7 in Study B5091009), a sample size of 263 evaluable subjects per lot will provide an overall 90% power to declare equivalence between all 6 comparisons for both toxin A and toxin B (see [Table 2](#)).

**Table 2. Power Analysis (Primary Immunogenicity Endpoint)**

Criteria	Neutralizing Antibody	Standard Deviation (Log Value)	Assume Observed Log GMC Difference	Number of Evaluable Subjects per Lot	Power a	Overall Power (3 Comparisons for Each Toxin)
95% CI for GMC ratio (any 2 lots) is between 0.5 and 2.0	Toxin A	0.899	0.2	263	>99.99%	>99.99%
	Toxin B	1.485	0.2	263	96.72%	90.47%
	Overall power (to meet equivalence for both toxin A and toxin B)					

Abbreviation: GMC = geometric mean concentration.

a. Using a 2-fold equivalence margin for GMC ratios at a 2-sided, 0.05 alpha level.

Assuming a maximum nonevaluable rate of approximately 20%, a total of 1316 subjects need to be enrolled to meet the primary objective, with a randomization ratio of 1:1:1:1 (Lot 1: Lot 2: Lot 3: placebo).

### 2.2.3. Schedule of Activities

The schedule of activities table provides an overview of the protocol visits and procedures.

**Table 3. Schedule of Activities**

Visit ID	Visit 1	Visit 2	Visit 3	Visit 4	Visit 5
Visit Description	Month 0 (Vax 1)	Month 1 (Vax 2)	Month 2 (Phone Contact)	Month 6 (Vax 3)	Month 7
Visit Window (Days)	1	28-42 Days After Visit 1	28-42 Days After Visit 2	140-168 Days After Visit 2	28-42 Days After Visit 4
Informed consent a	X				
Demography a	X				
Clinical assessment, including medical history a	X				
Record nonstudy vaccinations b	X	X	X	X	X
Measure and record height and weight a	X				
Oral temperature a	X	X		X	
Discuss contraceptive use b	X	X	X	X	
Confirm eligibility b	X	X	X	X	X
Review temporary delay criteria a	X	X		X	
Randomization a	X				
Blood draw for immunogenicity assessment b	X				X c
Vaccination	X	X		X	
Postvaccination observation (at least 30 minutes) and AE assessment	X	X		X	
Issue measuring device and thermometer, and provide instructions on their use, as required	X	X		X	
Assist the subject with downloading the app, or issue provisioned device	X				
Review e-diary completion requirements	X	X		X	

**Table 3. Schedule of Activities**

Visit ID	Visit 1	Visit 2	Visit 3	Visit 4	Visit 5
Visit Description	Month 0 (Vax 1)	Month 1 (Vax 2)	Month 2 (Phone Contact)	Month 6 (Vax 3)	Month 7
Visit Window (Days)	1	28-42 Days After Visit 1	28-42 Days After Visit 2	140-168 Days After Visit 2	28-42 Days After Visit 4
Record AEs/SAEs	X	X	X	X	X
Telephone contact			X		
Review e-diary data d		←			→
Collect e-diary					X

Abbreviations: e-diary = electronic diary; Vax = vaccination; ←→ = ongoing/continuous event.

- Prior to vaccination.
- Prior to vaccination, if at a vaccination visit.
- Any AEs occurring up to 48 hours after blood draw must be recorded on the case report form (CRF).
- E-diary data review is ongoing during subject e-diary data-entry periods (7 days after each vaccination) via an internet-based portal.

### 3. ENDPOINTS AND BASELINE VARIABLES: DEFINITIONS AND CONVENTIONS

#### 3.1. Primary Endpoints

- C difficile* toxin A- and toxin B-specific neutralizing antibody levels for each lot, expressed as GMCs (neutralization units/mL) at Month 7.
- Local reactions (pain, erythema, and induration), as self-reported in electronic diaries (e-diaries) for up to 7 days following each dose of investigational product.
- Systemic events (fever, vomiting, headache, fatigue, new or worsening muscle pain, and new or worsening joint pain), as self-reported in e-diaries for up to 7 days following each dose of investigational product.
- Nonserious AEs from signing of the informed consent document (ICD) to 1 month after receipt of the third dose of investigational product.
- SAEs from signing of the ICD to 1 month after receipt of the third dose of investigational product.

CCI

C [REDACTED]  
C [REDACTED]  
I [REDACTED]  
[REDACTED]  
CCI [REDACTED]  
[REDACTED]

### **3.4. Baseline Variables**

#### **3.4.1. Demographics, Physical Examination, and Medical History**

Baseline demographic variables for subjects are age at enrollment (signing of the ICD), sex, race, and ethnicity. Age will be calculated as (date of the ICD – date of birth + 1)/365.25 and truncated to the nearest integer less than or equal to the calculated value.

A clinical assessment, including medical history, will be performed on all subjects at Visit 1 to establish a baseline. Significant medical history and observations from any physical examination, if performed, will be documented in the case report form (CRF). Medical history for the subjects will be categorized according to the current version (at the time of reporting) of the Medical Dictionary for Regulatory Activities (MedDRA).

#### **3.4.2. Nonstudy Vaccines and Concomitant Medications**

Subjects will be asked to provide a history with the name(s) and date(s) for all vaccinations received from 28 days prior to enrollment until completion of the study. No vaccines other than investigational product should be administered within 28 days before and 28 days after each study vaccination (administered at Visits 1, 2, and 4). Exceptions to this are the seasonal influenza vaccine and pandemic influenza vaccine, which can be given at least 14 days prior to or 14 days after the administration of investigational product. No additional concomitant medications will be recorded.

#### **3.4.3. Baseline Serostatus**

An individual subject's baseline serostatus (prior to the first vaccination) will be defined based on the lower limit of quantitation (LLOQ) values for toxin A– and toxin B–specific neutralizing antibody levels as outlined below.

- Toxin A (positive): baseline toxin A–specific neutralizing antibody level  $\geq$  LLOQ for toxin A–specific neutralizing antibody level
- Toxin A (negative): baseline toxin A–specific neutralizing antibody level  $<$  LLOQ for toxin A–specific neutralizing antibody level
- Toxin B (positive): baseline toxin B–specific neutralizing antibody level  $\geq$  LLOQ for toxin B–specific neutralizing antibody level

- Toxin B (negative): baseline toxin B-specific neutralizing antibody level < LLOQ for toxin B-specific neutralizing antibody level

In addition, the following 4 groups will also be defined.

- Toxin A (positive)/toxin B (positive): baseline serostatus is positive for both toxin A and toxin B
- Toxin A (positive)/toxin B (negative): baseline serostatus is positive for toxin A and negative for toxin B
- Toxin A (negative)/toxin B (positive): baseline serostatus is negative for toxin A and positive for toxin B
- Toxin A (negative)/toxin B (negative): baseline serostatus is negative for both toxin A and toxin B

CCI

### 3.5. Safety Endpoints

#### 3.5.1. Adverse Events

Safety endpoints will include Pfizer standard safety endpoints collected in the study. An adverse event (AE) is defined as any untoward medical occurrence and can therefore be any unfavorable and unintended sign (including an abnormal laboratory finding), symptom, or disease, whether or not related to the subject's participation in the study.

The time period for actively eliciting and collecting AEs for each subject begins from the time the subject provides informed consent through and including Visit 5 (Month 7). For subjects who are screen failures, the active collection period ends when screen failure status is determined.

Overall AEs by category (any AE, related AE, severe AE, serious AE, etc) will be summarized by the pooled lots and the control group from the date of the first dose to 1 month after receipt of the third dose of investigational product. AEs and SAEs will be summarized by the pooled lots and the control group from the date of the first dose to 1 month after receipt of the third dose of investigational product, by MedDRA term. SAEs will also be summarized by the pooled lots and the control group from the date of the first dose throughout the entire study by MedDRA term. In addition, a subject-level listing of all AEs reported will also be provided. In general, all summaries will present the number and percentage of subjects experiencing at least 1 event and the number of events for the pooled lots and the control group, and the exact 2-sided 95% confidence intervals (CIs).

The 3-tier approach will be used for the AE summary. Under this approach, AEs are classified into 1 of 3 tiers. Only for Tier 1 and Tier 2 AEs, the difference in the percentages between the *C difficile* vaccine (pooled lots) group and the placebo group, as well as the 2-sided 95% CI, will be provided. In addition, the p-value will be reported for Tier 1 events. CIs and p-values will be based on the Miettinen and Nurminen method.

**Tier 1 events:** These are prespecified events of clinical importance and, if any, are maintained in a list in the product's Safety Review Plan.

**Tier 2 events:** These are events that are not Tier 1 but are "common." A MedDRA preferred term (PT) is defined as a Tier 2 event if its incidence is  $\geq 1.0\%$  in at least 1 vaccine group (combined lots or placebo).

**Tier 3 events:** These are events that are neither Tier 1 nor Tier 2 events.

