5.1. Allocation to Investigational Product

Allocation of subjects to vaccine groups will proceed through the use of an interactive response technology (IRT) system (interactive Web-based response [IWR]) in a randomization ratio of 1:1:1:1 to each of the lots and control group. Study personnel (either

blinded or unblinded) will be required to enter or select information including but not limited to the user's identification (ID) and password, the protocol number, and the subject number. They will then be provided with a randomization number, vaccine assignment, and dispensable unit (DU) or container number. The IRT system will provide a confirmation report containing the subject number, randomization number, and DU or container number assigned. The confirmation report must be retained by the unblinded dispenser in the unblinded site files.

The study-specific IRT reference manual will provide the contact information and further details on the use of the IRT system.

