9.2. Immunogenicity Analysis

The immunogenicity data will be summarized according to the vaccine group (active vaccine and placebo) as received in the evaluable immunogenicity population, and according to the vaccine group as randomized in the modified intent-to-treat (mITT) population. Subjects receiving vaccine who did not follow their randomization assignment will be excluded from the evaluable immunogenicity population.

The *C difficile* toxin A– and toxin B–specific neutralizing antibody levels at each blood sampling time point will be summarized by GMCs (any *C difficile* toxin A– or toxin B–specific neutralizing antibody level that is below the lower limit of quantitation [LLOQ] will be assigned as $0.5 \times \text{LLOQ}$) and the associated 95% confidence intervals (CIs). The GMC will be calculated as the mean of the assay results after making the logarithm transformation and then back transformation to its original scale. Two (2)-sided 95% CIs will be constructed by back transformation of the CI for the mean of the logarithmically transformed assay results computed based on the Student's t distribution.

Exact 2-sided 95% CIs will be compiled using the Clopper-Pearson method for any proportions of subjects with *C difficile* toxin A– or toxin B–specific neutralizing antibody level \geq cutoff (LLOQ).

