9.3. Safety Analysis

The safety population will include all subjects who receive at least 1 dose of an investigational product. For the safety analysis, subjects will be analyzed according to the investigational product received. A descriptive summary will be presented for each vaccine lot, the combined vaccine lots, and the control group. For Tier 1 and Tier 2 events, the comparison between the pooled lots and control group will be performed.

Point estimates and the exact 2-sided 95% CIs will be compiled using the Clopper-Pearson method for proportions of subjects reporting each event.

The proportions of subjects reporting local reactions at the injection site (pain, erythema, and induration), and systemic events (fever, vomiting, headache, fatigue, new or worsening muscle pain, and new or worsening joint pain), on any day within the 7-day period after vaccination will be descriptively summarized by vaccine group and by each vaccination. Severities of local reactions and systemic events reported after each vaccination will also be descriptively summarized by vaccine group. Exact 2-sided 95% CIs will be presented with the proportions.

AEs and SAEs will be categorized according to Medical Dictionary for Regulatory Activities (MedDRA) terms. AEs will be summarized by vaccine group from signing of the ICD to 1 month after receipt of the third dose of investigational product. SAEs will be summarized by vaccine group from signing of the ICD to 1 month after receipt of the third dose of investigational product, and throughout the entire study. In general, all summaries will present the number and percentage of subjects experiencing at least 1 event and the number of events for each vaccine group, and the exact 2-sided 95% CIs.

The 3-tier approach will be used for the AE summary. Detailed analysis of each tier will be described in the SAP.

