### **5.2.2. Analyses for Continuous Data**

The *C difficile* toxin A– or toxin B–specific neutralizing antibody levels at each blood sampling time point will be summarized by GMCs and the associated 95% CIs for each vaccine group and also for combined active arms. The GMC will be calculated as the mean of the assay results after making the logarithm transformation and then exponentiating the result. Two-sided 95% CIs will be constructed by obtaining the CI for the mean of the logarithmically transformed assay results based on the t-distribution, and then exponentiating the limits.

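### SAP 3.5.1 specifies AE and SAE summaries for pooled lots and control only, although Protocol 9.3 plans a descriptive safety summary for each lot and the readable text gives no reason for the change.

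*SAP*

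**What the plan says.** Protocol 9.3 first defines the safety population and then states: "A descriptive summary will be presented for each vaccine lot, the combined vaccine lots, and the control group". The next sentence reserves the pooled-lots comparison with control for Tier 1 and Tier 2 events. Later in the section the AE sentence reads "AEs will be summarized by vaccine group from signing of the ICD to 1 month after receipt of the third dose".

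SAP 3.5.1 makes four statements about AE and SAE tables:

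- overall AE categories: pooled lots and control;
- events by MedDRA term: "AEs and SAEs will be summarized by the pooled lots and the control group";
- SAEs over the whole study: "SAEs will also be summarized by the pooled lots and the control group";
- general content of the tables (subjects, percentages, event counts, exact intervals): pooled lots and control.

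None of the four mentions an individual lot. A near-copy of the protocol's each-lot sentence appears in SAP 3.5.3, Reactogenicity Data. SAP 6.1.3 names no groups for the AE and SAE endpoints. SAP 6.5 refers to a sponsor reporting standard that is not part of the documents.

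**The concern.** AEs and SAEs are primary safety endpoints, and the trial exists to show that three lots behave alike. A programmer following SAP 3.5.1 as written would build AE tables with two columns. An excess confined to one lot would enter the pooled column at one third of its absolute size and could not be told from an even spread. Where the SAP wants output by lot, as for reactogenicity, it says so explicitly. Its silence on lots in the AE section therefore reads as a change of plan, and no reason is given in the readable text.

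**Working it through.** **Does the protocol's each-lot sentence cover AEs?** It sits in the general safety paragraph with no restriction to e-diary data. The sentence after it concerns Tier 1 and Tier 2 events, and Protocol 9.3 says the three-tier approach is for AEs. So the paragraph covers AEs.

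**Does *vaccine group* settle the grouping?** No, because the term is used in two ways.

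- As two groups: Protocol 9.2 has "summarized according to the vaccine group (active vaccine and placebo) as received", and the Tier 2 definition in SAP 3.5.1 also contrasts the lots taken together with placebo.
- As separate arms: Protocol 5.1 allocates subjects to vaccine groups "in a randomization ratio of 1:1:1:1 to each of the lots and control group", and SAP 5.2.2 gives antibody results "for each vaccine group and also for combined active arms".

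The plan for AE summaries by lot therefore rests on the explicit each-lot sentence in Protocol 9.3.

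**Is a reason given?** The readable entries in SAP Table 1 that touch AEs cover the start date, the deleted 30-minute analysis and the analysis populations. None concerns grouping by lot. The Version 2 row and part of the Version 3 row are redacted and cannot be checked.

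**Group sizes.** Protocol 9.1 gives 263 evaluable subjects per lot and 20% nonevaluable: 263 / 0.80 = 328.75, rounded up to 329; 4 × 329 = 1316, the stated total. If all are dosed, the pooled vaccine column has 3 × 329 = 987 subjects.

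**What pooling shows.** The counts below are assumed for illustration: nine subjects with the same event. Intervals are Clopper-Pearson, with lower limit the 0.025 quantile of Beta(r, n − r + 1) and upper limit the 0.975 quantile of Beta(r + 1, n − r). For r = 0 the upper limit is 1 − 0.025^(1/329) = 1.11%.

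| Split over lots | Pooled column | Highest lot | Each other lot |
|---|---|---|---|
| 9/0/0 | 9/987 = 0.91% (0.42 to 1.72) | 9/329 = 2.74% (1.26 to 5.13) | 0/329 = 0% (0 to 1.11) |
| 5/2/2 | 9/987 = 0.91% (0.42 to 1.72) | 5/329 = 1.52% (0.50 to 3.51) | 2/329 = 0.61% (0.07 to 2.18) |
| 3/3/3 | 9/987 = 0.91% (0.42 to 1.72) | 3/329 = 0.91% (0.19 to 2.64) | 3/329 = 0.91% (0.19 to 2.64) |

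With equal lot sizes the pooled rate is the mean of the three lot rates, so the 9/0/0 case is diluted to 2.736% / 3 = 0.912%. That is below the 1.0% Tier 2 cutoff in SAP 3.5.1. Unless the event were on the Tier 1 list or reached 1.0% on placebo, it would be Tier 3 and no risk difference would be shown.

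**What chance alone does.** If the lots are truly equal, each of nine cases falls in a given lot with probability 1/3. Two lots cannot both hold five or more, so for k ≥ 5:

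P(largest lot ≥ k) = 3 × Σ_{j ≥ k} C(9, j) × 2^(9 − j) / 3^9, with 3^9 = 19683.

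- k = 5: 3 × (2016 + 672 + 144 + 18 + 1) / 19683 = 8553 / 19683 = 43.5%.
- k = 7: 3 × (144 + 18 + 1) / 19683 = 489 / 19683 = 2.5%.
- k = 9: 3 / 19683 = 0.015%.

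Lot columns would therefore expose a strong concentration but could not separate a mild one from chance.

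**The case against.** The best counter-argument is that the plan already covers this and the sentence is merely misplaced. SAP 3.5.3 carries over both protocol sentences, the each-lot summary and the Tier 1/2 comparison, and the SAP defines tiers only for AEs. The last paragraph of 3.5.3 separately gives by-lot summaries of local reactions and systemic events, so the general sentence is largely redundant if it covers e-diary data alone. SAP 4.3 also places misdosed subjects in the AE summary by the first dose or lot received, which for a wrong-lot error matters only if AE tables are split by lot. This reading is arguable. However, the heading and opening of 3.5.3 limit it to e-diary data, and the 4.3 rule is also needed for vaccine/placebo errors, so it fits pooled tables too. Even if by-lot AE tables were intended, SAP 3.5.1 says otherwise four times and needs the same edit.

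Other points stand in part. SAP section 2 allows the SAP to modify protocol plans, so there is no breach. Redacted text or the sponsor's reporting standard may contain a reason or a layout that cannot be seen here. The subject-level AE listing, review by the external data monitoring committee and by-lot reactogenicity tables all reduce the gap, although a listing gives no rates or intervals by lot and committee review is not the final analysis. The gain is also limited by chance variation, as the 43.5% figure shows. These points keep the priority modest; they do not remove the mismatch.

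**Conclusion.** The concern holds. In the readable text, SAP 3.5.1 narrows the AE and SAE display from each lot, combined lots and control to pooled lots and control, without explanation. The consequence is descriptive: an excess in one lot is shown at one third of its absolute size, and quite different distributions over the lots give identical table entries. The illustration assumes nine cases and that all 1316 subjects are dosed equally across groups; neither is a forecast. The lot-consistency test, its power, the sample size and alpha do not depend on this point. It should be fixed because the endpoints are primary and the remedy is cheap. Confidence is medium, because of the redactions and the loose use of *vaccine group*.

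**What to change.** In SAP 3.5.1 and 6.1.3, add Lot 1, Lot 2 and Lot 3 columns beside pooled lots and placebo, giving n, percentage, number of events and exact two-sided 95% CI. Do this at least for the overall AE categories and for AEs and SAEs by MedDRA term. Place subjects by the first-dose rule in SAP 4.3, unchanged. Label the lot columns descriptive, with no test between lots. Leave the tier definitions and the pooled-versus-placebo comparison as they are. If the sponsor prefers pooled tables, the minimum is to state that choice and its reason in SAP Table 1.

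The cost is three more columns in tables already planned, with no new data, subjects or tests. The drawback is that chance differences between lots will be visible across many MedDRA terms, so the text should tell readers not to interpret isolated imbalances as lot effects.
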